3.1.2 Secondary Objectives

The secondary objectives of the study are to:

- Explore patient-, practitioner-, practice- and tooth- level characteristics that may contribute to practitioners' selected treatment(s) and approach(es) to care, and
- Characterize patients' satisfaction with the received treatment of DH.

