3.2 Study Outcome Measures

3.2.1 Primary Outcomes

To characterize diagnosis and treatment of DH in the practice setting, practitioners' preferred methods of diagnosing and treating DH will be ascertained via a practitioner

online questionnaire to be completed upon study enrollment and via practitioner data collection forms during patient visits.

Diagnosis of dentin hypersensitivity:

Online practitioner questionnaire: Practitioners' preferred diagnostic procedures that are usually implemented when diagnosing DH in the practice setting will be ascertained. These will include: spontaneous patient report, patient report after dentist's query, applying air blast, applying cold water, scratching dentin with dental explorer, requesting numeric descriptor of pain, requesting visual scale descriptor of pain, and using an electric pulp tester.

Treatment modalities:

Online practitioner questionnaire: Practitioners' preferred method of treatment of DH and the rationale for the elected treatment or treatments will be ascertained. Questions will include preferred treatment modalities (see below) and approach(es) to treatment of DH (i.e., providing multiple treatments at one time, one treatment or staged approach, no treatment, and/or no advice).

Patient visit(s): The usual and customary treatment(s) for DH utilized by the participating practitioner will be applied or prescribed and recorded.

The following groups of treatment modalities will be ascertained:

1. Fluoride products (gels, varnishes, pastes, rinses)
2. Desensitizing over the counter (OTC) Potassium nitrate toothpastes
3. Glutaraldehyde/HEMA products
4. Bonding agents
5. Sealants
6. Restorative treatments
7. Lasers
8. Oxalates
9. No treatment
10. Advice
11. Other

Patient-reported pain outcomes:

Patient visit(s) and follow-up: Patient-reported pain outcomes will be assessed by changes in patient report of pain intensity, duration, and frequency. Patients' perception of pain will be assessed by the Visual Analog Scale (VAS) at baseline, 1 week-, 4 weeks- and 8 weeks- post-baseline. Duration, intensity, tolerability and pain description changes will be assessed by means of the Labeled Magnitude (LM) scales at baseline, 1 week-, 4 weeks- and 8 weeks- post-baseline (Heaton et al., 2013). If patients return

for a second- or third-line of treatment, these pain assessments will be implemented also at 1, 4 and 8 weeks after the initiation of the second- or third-line of treatment.

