3.2.2 Secondary Outcomes

The proposed study will be conducted in six regions of the National Dental PBRN, allowing for a comparison among regions in relation to practitioners' approach(es) to care and treatment of DH based on the patient-, practitioner-, practice- and tooth- level characteristics. To explore the association between the above level characteristics and approach(es) to treatment for DH listed above, several patient-, practitioner-, practice- and tooth- level characteristics will be collected at baseline.

Patient characteristics:

Because this objective will explore characteristics that may contribute to practitioners' selected treatment(s) and approach(es) to care, the practitioner will be asked about the following patient variables at/or soon after the baseline visit:

Patient's predisposing variables: prior periodontal surgery and/or scaling and root planing, recent bleaching history, previous DH episodes and previous/current treatment modalities if any.

Patient's enabling variables: out-of-pocket cost for treatment and/or follow-up appointments after considering dental insurance coverage.

Practitioner characteristics:

The following practitioner variables will be collected upon enrolling in the National Dental PBRN by means of the enrollment questionnaire: age, gender, race/ethnicity, and year of graduation from dental school.

Knowledge about the etiology of DH and predisposing factors related to DH will be ascertained in the practitioner online questionnaire at study enrollment.

Practice characteristics:

The following practice variables will be collected from the practitioner as he/she enrolls in the National Dental PBRN by means of the enrollment questionnaire: practice size, location, practice business, wait time for new patients to be seen, number of patient visits per week, and hours of patient care per week.

Tooth (teeth) characteristics:

The following patient sensitive tooth (teeth) variables will be collected at the baseline visit: number of teeth that are sensitive, tooth (teeth) location, gingival recession, exposed dentin, recent periodontal surgery relating to the sensitive tooth (teeth), number of remaining teeth (surrogate for oral/dental functioning), whether or not the sensitive tooth has a restoration and, if so, the type of restoration, and location and number of surfaces restored.

Patient Satisfaction:

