Analysis approach: Patients' ratings of dentin sensitivity will be compared across the observation times using generalized linear models. Terms representing individual practitioners and patients will be included as random effects in the analytic model, to account for correlation among multiple patients per practitioner and multiple observation times per patient. Terms representing observation time and treatment modality will be included as fixed effects. The statistical test that will be of primary interest will be the time by treatment interaction term, which would reflect different trajectories of reported pain levels among the treatment modalities. This analysis model will also provide group-specific means and standard errors, accounting for clustering, which will allow estimation of trajectories of pain outcomes across time. Plots of adjusted means across time will be constructed for each of the subgroups in the analysis, along with appropriate measures of variability. It should be noted that the measures of change within individual treatment groups do not separate change due to treatment from that due to natural time course or other causes. Comparisons of means between treatment groups do reflect the differences between treatment effects because the effects of causes that are common to both groups are removed in the calculation of the differences.

Depending on the nature of the distribution of the reported VAS scores, this analysis will be implemented either as a general linear mixed-model, if the residual distribution is approximately normal, or a generalized mixed-model, if a non-normal distribution is required. Other approaches that may be considered for the analysis of non-normal measures include using data transformations or analysis of ranked data.

Analysis plan for Secondary Objectives:

#1. To explore patient-, practice- and tooth- level characteristics that may contribute to practitioners' selected treatment(s) and approach(es) to care.

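### Section 11.2 reads differences between practitioner-chosen treatments as treatment effects, although causes that differ between the groups do not cancel

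*Protocol*

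**What the plan says.** The study does not assign treatment. Section 3.2.1 of the protocol: "The usual and customary treatment(s) for DH utilized by the participating practitioner will be applied or prescribed and recorded". Section 2.2 explains why a cohort was preferred to a randomised trial. The first secondary objective (section 3.1.2) reads: "Explore patient-, practitioner-, practice- and tooth- level characteristics that may contribute to practitioners' selected treatment(s) and approach(es) to care". Section 11.2 plans regressions of each modality on such variables.

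For the pain objective (primary objective 3), section 11.2 sets out the model in three statements:

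- "Terms representing observation time and treatment modality will be included as fixed effects".
- "Terms representing individual practitioners and patients will be included as random effects in the analytic model, to account for correlation".
- "The statistical test that will be of primary interest will be the time by treatment interaction term".

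It then cautions, correctly, that change within one treatment group mixes the effect of treatment with natural course and other causes. For differences between groups it takes the opposite line: "Comparisons of means between treatment groups do reflect the differences between treatment effects because the effects of causes that are common to both groups" drop out when the difference is formed.

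Two other places bear on this. Section 3.2.1 says that, as far as the data allow, pain outcomes will be described by age, gender, race/ethnicity and education. Section 3.2.2 lists dental-history variables ("prior periodontal surgery and/or scaling and root planing, recent bleaching history, previous DH episodes and previous/current treatment modalities if any") and tooth variables such as number of sensitive teeth, recession, exposed dentin and restorations. These are collected to explain treatment choice and are not linked to the pain model. The protocol nowhere mentions confounding.

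**The concern.** Taking a difference removes a cause only if it acts equally in both groups. Randomisation would make that a reasonable expectation. Here the modalities run from over-the-counter toothpaste through restorations to no treatment, and the practitioner picks among them. The protocol devotes an objective to which characteristics lie behind that choice, so it expects the groups to differ. Any such characteristic that also affects the course of pain stays in the between-group difference.

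The sentence therefore supports a causal reading of the main test of a primary objective. Section 2.2 expects the study to improve knowledge of which products are effective, and section 4 says the data may serve guidelines. A large sample does not help: it narrows the interval around a biased value.

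**Working it through.** **What the stated model removes.** Pain is rated at baseline and at 1, 4 and 8 weeks (section 3.2.1). With baseline as one of the observation times, a stable difference in pain level between modality groups goes into the modality main effect and not into the time by treatment interaction. Three things are not removed:

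1. Regression to the mean, if groups start at different pain levels.
2. Courses that differ by severity or tooth condition.
3. Switching after poor response. Under section 4, patients without relief may go on to a second or third line, and follow-up of the earlier treatment then ends.

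The practitioner and patient random effects are included for correlation. The adjusted means in section 11.2 do not imply covariate adjustment either: section 11.1 introduces least-squares adjusted means to handle missing values.

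**Inputs from section 11.1.** 180 dentists, 14 patients each (2,520), ICC 0 to 0.05, Type I error 5% (taken as two-sided), power 80%.

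**The plan's own figure first.** Effective N = 180m / (1 + (m − 1) × ICC). The standard error of a difference between two equal groups, in SD units, is √(2 / (N/2)) = 2/√N. Detectable difference = (1.960 + 0.842) × 2/√N.

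- m = 20, ICC 0: N = 3,600, giving 0.0934 SD (stated 0.095).
- m = 10, ICC 0.05: N = 1,800/1.45 = 1,241.4, giving 0.159 SD (stated 0.160).

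Both agree within about 2%. At the planned m = 14:

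- ICC 0: N = 2,520, detectable difference 0.112 SD.
- ICC 0.05: N = 2,520/1.65 = 1,527.3, detectable difference 0.143 SD.

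**Illustration with zero true effect.** The protocol gives no size for the bias, so b is assumed. One way to reach 0.15 SD is a factor that shifts pain change by 0.5 SD and is present in 70% of one group and 40% of the other: 0.5 × (0.70 − 0.40) = 0.15. Rejection probability = Φ(b/SE − 1.96) + Φ(−b/SE − 1.96).

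- Two equal groups: SE = 2/√N = 0.0512 (ICC 0.05) or 0.0398 (ICC 0). For b = 0.15, b/SE = 2.93 or 3.76, giving 83% or 96%.
- One pair among four equal groups: SE = √(8/N) = 0.0724 or 0.0563, giving 54% or 76%.

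| Assumed bias (SD) | Two groups, ICC 0.05 / 0 | One pair of four, ICC 0.05 / 0 |
|---|---|---|
| 0.05 | 16% / 24% | 11% / 14% |
| 0.10 | 50% / 71% | 28% / 43% |
| 0.15 | 83% / 96% | 54% / 76% |
| 0.20 | 97% / 99.9% | 79% / 94% |

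With the 20% loss considered in section 11.1 (2,016 patients), the 0.15 SD row becomes 78% / 92% and 49% / 66%.

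**Simulation.** 180 dentists, 14 patients each, ICC 0.05, no treatment effect, groups differing by 0.25 SD in a baseline factor correlated 0.3 or 0.5 with pain change, analysed within dentist, 600 runs per setting. False positives were 49% and 85% without the factor in the model, and 4% and 6% with it. Accounting for the dentist alone does not remove the bias.

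**The case against.** The strongest reply is that only the protocol is available and covariate lists commonly belong in the SAP. Section 11.2 names terms that will be included and does not say that there are no others. This stands: the missing covariate list is not by itself a defect. It does not protect the sentence on treatment effects, which is a stated rule and is wrong as it reads.

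A reader might infer that the model does nothing about severity, so that any baseline difference in pain passes for an effect. The documents do not support that, because the interaction test removes stable level differences. A reader might also infer that confounded results will certainly be published as effectiveness. The objective is framed as characterising outcomes, section 11 describes an estimation-driven study, and the guideline language is conditional. The sentence invites the causal reading but does not make it certain. Nor did patients select their own treatment groups; the practitioner's choice is what is studied.

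The rates are also open to challenge. The bias is assumed, two groups is the most sensitive layout, and a two-mean test stands in for the interaction test. No multiplicity adjustment is made, because the plan's own figures reproduce without one; an adjusted test would reject less often. Hence the range in the table: at 0.05 SD the excess over 5% is modest.

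**Conclusion.** The sentence in section 11.2 is incorrect for practitioner-chosen treatment and conflicts with the first secondary objective, which expects choice to depend on characteristics that may differ between the groups. The fixed effects stated do not repair it, and the time by treatment test repairs it only in part.

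The size cannot be determined from the documents. With an assumed bias of 0.15 SD and no true effect, a false difference is declared 83% to 96% of the time with two equal groups and 54% to 76% for one pair of four; at 0.05 SD, about 11% to 24%. These figures assume the plan's ICC range, 14 patients per dentist, full follow-up and an unadjusted two-sided 5% test. They show that the study is sensitive to small biases. They do not show that biases of this size will occur.

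**What to change.** Withdraw or qualify the sentence, and state that differences between modalities are associations subject to confounding by indication.

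Add an adjusted version of the Objective 3 model, in the protocol or the SAP, using pre-treatment variables already collected, with time interactions where the data support them:

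- baseline pain, for example by modelling follow-up or change given baseline;
- number of sensitive teeth, and patient-level summaries of recession, exposed dentin and restoration (the pain ratings are per patient, section 7.2, so a summary rule is needed);
- periodontal and bleaching history, previous hypersensitivity and its treatment;
- age, gender, race/ethnicity and education;
- practitioner and practice characteristics.

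Leave out the out-of-pocket treatment cost in section 3.2.2, since it may follow from the modality chosen. Report unadjusted and adjusted trajectories side by side. Acknowledge residual confounding, and that baseline adjustment does not deal with switching after poor response.

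No new data or change of sample size is needed. The costs are weaker causal language and many more parameters once multi-category covariates interact with time, which may limit adjustment for rarely used modalities.

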12 SOURCE DOCUMENTS AND ACCESS TO SOURCE DATA/DOCUMENTS

Each participating site will maintain appropriate medical and research records for this study, using the principles of good clinical practice and complying with regulatory and institutional requirements for the protection of confidentiality of subjects. Each site will permit authorized representatives of NIDCR and regulatory agencies to examine (and when required by applicable law, to copy) research records for the purposes of quality assurance (QA) reviews, audits, and evaluation of the study safety, progress and data validity.

The following clinical records will be considered source documents where they are used to complete case report forms (CRFs): clinical and office charts and recorded data from automated instruments.

The following CRFs or portions of CRFs will be considered source documents, as it is not expected that all patients' clinical charts would contain the exact information collected on these CRFs: Baseline Exam, Symptomatic Exam, Patient History, all Pain Assessments, and questions on ethnicity, race, and highest level of education from the Patient Demographics CRF.

All study source documents must be maintained in a secure manner, and practice personnel and network personnel will have access to source documents. Study source documents may include clinical records and as such are subject to Health Insurance Portability and Accountability Act (HIPAA) regulations. These records will be subject to examination and copying as stated elsewhere in this section.

13 QUALITY CONTROL AND QUALITY ASSURANCE

For the QA/quality control (QC) activities associated with data collection and processing, the CC will develop a data management plan in which the specific data QA/QC procedures will be provided. The procedures will include the development of automatic data quality checks in the database system and the processes related to the data manual review, discrepancy management, delinquent data handling, data updates, data verification and approval, and database audit. A work instruction will be provided to the RCs at the RAS with the specified tasks, timelines of completing the tasks, roles and responsibilities. The Data Manager at the CC will work with the RCs to ensure that all procedures are followed and that the data are checked according to the validation requirements specified in the study protocol. The RCs will perform QA review of a percentage of CRFs, as specified in the data management plan. In these QA reviews, data entered into the web-based system will be compared against CRFs. Mismatches will be corrected in the web system. At the end of the study, the RCs will ensure that all data collected by the regional offices are entered and cleaned. The Data Manager at the CC will verify the completion of data entry and clarifications by running monitoring reports. Once confirmed that the data entry is complete and the data are verified and approved for accuracy, the database will be locked for final analysis. Although no interim analysis is planned, if interim data analysis is needed during the study period, the Data Manager will coordinate the activities with the RCs and the Statistician. The interim datasets will be provided with the data collected as of the specified date. The data in those datasets will be cleaned if possible but may contain pending issues which will be provided to the Statistician if requested. The datasets will be provided to the Statistician via secure data transfer method. The Quality Management Plan is detailed in Appendix C.

14 ETHICS/PROTECTION OF HUMAN SUBJECTS

14.1 Ethical Standard

The investigator will ensure that this study is conducted in full conformity with the principles set forth in The Belmont Report: Ethical Principles and Guidelines for the Protection of Human Subjects of Research, as drafted by the US National Commission for the Protection of Human Subjects of Biomedical and Behavioral Research (April 18, 1979) and codified in 45 CFR Part 46.

14.2 Institutional Review Board

The protocol, consent form(s), recruitment materials and all participant materials will be submitted to the regional IRBs for review and approval. Approval of both the protocol and the consent form must be obtained before any participant is enrolled. Any amendment to the protocol will require review and approval by the IRB before the changes are implemented in the study.

It is recognized that this protocol must receive the approval of six or more different IRBs, and each may have different criteria for subject consent. Therefore, different regions may have slightly varied informed consent procedures. For the purposes of this minimal risk, non-intervention study, any of the following will be considered acceptable by the study investigators, at the discretion of the responsible IRB: waiver of informed consent with information sheet explained and provided; verbal consent; verbal consent for initial data collection followed by written consent; written information sheet provided prior to or at the time of data collection; or written consent and authorization.

14.3 Informed Consent Process

Informed consent is a process that is initiated prior to the individual agreeing to participate in the study and continues throughout study participation. Extensive discussion of risks and possible benefits of study participation will be provided to participants and their families, if applicable. If required by the responsible IRB, a consent form describing in detail the study procedures and risks will be given to the participant. Consent forms will be IRB-approved, and the participant is required to read and review the document or have the document read to him or her. The investigator or designee will explain the research study to the participant and answer any questions that may arise. The timing for the signing of the consent form required by the responsible IRB will be adhered to if written consent is required (i.e., before or after other study procedures). Participants will be given the opportunity to discuss the study with their surrogates or think about it prior to agreeing to participate. They may withdraw consent at any time throughout the course of the study. A copy of the informed consent document will be given to participants for their records. The rights and welfare of the participants will be protected by emphasizing to them that the quality of their clinical care will not be adversely affected if they decline to participate in this study.

The consent process will be documented in the clinical or research record.

Participating practices will designate the individual(s) who will execute informed consent for the study. In most cases this will be the dentist practitioner(s). Any personnel who will be assigned to perform consent procedures will be defined as study personnel and will complete required IRB training. Consent procedures will be performed in the participating practice prior to enrolling a patient into the study.

14.4 Exclusion of Women, Minorities, and Children (Special Populations)

Children 19 years of age and older will be included in this study. Only permanent teeth are of interest to ensure that enrolled teeth can remain for the duration of the study.

14.5 Participant Confidentiality

Participant confidentiality is strictly held in trust by the investigators, study staff, and the sponsor(s) and their agents.

The study protocol, documentation, data, and all other information generated will be held in strict confidence. No information concerning the study or the data will be released to any unauthorized third party without prior written approval of the sponsor.

Practitioners and patients will be assigned unique identification numbers, which will be used to maintain study records and organize data transcripts. A file linking practitioners' and patients' names with their unique identification number will be kept in a password-protected file on the CC's computer, separate from all other research records.

The study monitor and other authorized representatives of the sponsor may inspect all study documents and records required to be maintained by the investigator, including but not limited to, dental records (e.g., office, clinic, or hospital) for the study participants. The clinical study site will permit access to such records.

